8.2 Demographics and baseline characteristics

Demographics and baseline characteristics data will be listed and summarized by treatment group using the ITT population.

8.3 Protocol Treatment

Duration of treatment exposure, cumulative dose and dose intensity will be summarized by treatment group using the Safety population. The patients with dose modifications will be presented by treatment group, along with reasons for the dose change.

8.4 Safety Endpoints

Adverse Events - The latest version of the Medical Dictionary for Regulatory Activities (MedDRA) will be used to code all adverse events to a preferred term and system organ class. Adverse events will be graded using the Common Terminology Criteria for Adverse Events (NCI CTCAE v4.0). Patient's incidence of adverse events will be tabulated by system organ class, preferred term and toxicity grade by treatment arm. Adverse events leading to death or drug discontinuation, drug related and serious adverse events will also be summarized by treatment arm.

Detailed listings for all adverse events will also be provided.

Laboratory parameters - Laboratory parameters, graded according to the NCI CTCAE v4.0, will be summarized at baseline, along visits and at the end of trial treatment by treatment arm. Tables of shifts in toxicity will also be provided.

Other Safety Data – Vital signs (weight and blood pressure), ECOG and LVEF will be summarized at baseline, along visits and at the end of trial treatment by treatment arm. Tables of shifts in toxicity will also be provided when applicable.

8.5 Interim and Final Analyses

The following analyses are planned:

A first analysis of safety was performed on the first 20 patients who complete 28 days of treatment. The steering committee reviewed this formal analysis.

The final analysis will be performed when all patients discontinue the trial.

8.6 Criteria for trial termination

The trial will stop once the last patient reaches end of trial treatment visit (30 days post last drug intake or 30 November 2018 whichever occurs first).

9. ADMINISTRATIVE, ETHICAL AND REGULATORY STANDARDS

9.1 Steering Committee

The Study Steering Committee (SSC) of the trial was set-up and operated as per TRIO SOPs. The SSC had the sole responsibility for the scientific conduct and integrity of the trial. Responsibilities included development and approval of the protocol document, monitoring of accrual, compliance and safety during the conduct of the trial. The SSC will be solely responsible for the analysis, interpretation and public disclosure of the results of the trial in accordance with the statistical plan.

Note: No additional SSC has taken place since the release of the previous amendment (09 May 2016) and no further SSC will take place after the release of this amendment.

9.2 Ethical Conduct of the Trial

This clinical trial was designed and shall be implemented and reported in accordance with the protocol, the ICH Harmonized Tripartite Guidelines for Good Clinical Practice, with applicable local regulations (including European Directives 2001/20/EC and 2005/28/EC and the US Code of Federal Regulations Title 21), and with the ethical principles laid down in the Declaration of Helsinki.

9.3 Institutional Review Board/Independent Ethics Committee (IRB/IEC)

The final approved protocol and its amendment and the informed consent statement /addendum will be reviewed by a properly constituted Ethics Committee/IRB. The Ethics Committee's/Board's decision concerning the conduct of the trial will be made in writing to the investigator and a copy of this decision will be provided to TRIO.

Particular attention is drawn to the FDA's regulation regarding the IRBs. By signing the "Statement of Investigator" form (Form 1572), the investigator provides TRIO with the necessary assurance that an IRB is responsible for the initial and continuing review and approval of the proposed clinical trial in accordance with these regulations when applicable.

The investigator will agree to make required progress reports to the Ethics committee/IRB, as well as report any serious adverse events, life-threatening problems or deaths. The Ethics Committee/IRB will be informed of serious adverse events in other clinical studies conducted with the trial drug by the investigator or the Sponsor according to the local regulations. The Ethics Committee/IRB must be informed by the investigator of the termination of the trial.

9.4 Compliance with the protocol and protocol amendments

Investigators ascertain they will apply due diligence to avoid protocol deviations. Under no circumstances should the investigator contact TRIO or its agents, if any, monitoring the trial to request approval of a protocol deviation, as no authorized deviations are permitted. If the investigator feels a protocol deviation would improve the conduct of the trial this must be considered a protocol amendment, and unless such an amendment is agreed upon by TRIO and approved by the IRB/IEC it cannot be implemented. All significant protocol deviations will be recorded and reported in the Clinical Study Report (CSR).

Any modifications to the protocol which may impact on the conduct of the trial, potential benefit of the patient or may affect patient safety, including changes of trial objectives, trial design, patient population, sample sizes, trial procedures, or significant administrative aspects will require a formal amendment to the protocol. Such amendment will be agreed upon by TRIO, and approved by the Ethics Committee/IRB and Health Authorities where required, prior to implementation. Only amendments that are required to eliminate an immediate hazard to patients for patient safety can be implemented prior to IRB/IEC approval. Notwithstanding the need for approval of formal protocol amendments, the investigator is expected to take any immediate action required for the safety of any patient included in this trial, even if this action represents a deviation from the protocol. In such cases, TRIO should be notified of this action and the IRB/IEC at the trial site should be informed.

9.5 Monitoring, auditing and inspecting

TRIO or its representatives must be allowed to visit all trial site locations periodically to assess the data, quality, and trial integrity. On site, they will notably review trial records and **directly** compare them with source documents, review regulatory documents, discuss the conduct of the trial with the investigator, verify trial drug accountability, and verify that the facilities remain acceptable.

9.6 Recording, processing and retention of data

An investigator will be required to prepare and maintain adequate case histories designed to record all observations and other data pertinent to the trial patients. All data reported on the CRF must be derived from source documents and as such be consistent with the source documents, or the discrepancies must be explained.

Data is entered and collected via an Electronic Data Capture System (EDC) using eCRFs (electronic Case Report Form). EDC is a validated system, designed for entry of data in a way that is attributable, secure, accurate, and in compliance with U.S. Food and Drug Administration (FDA) regulations for electronic records (21 CFR Part 11). Sites received training and got access to a manual for appropriate eCRF completion. All eCRFs should be completed by designated, trained site staff. The eCRFs should be reviewed and electronically signed and dated by the investigator or a designee. Only an identified and trained user may view the data, and their actions become part of the audit trail.

Sites are responsible for data entry into the EDC system. TRIO is responsible for data management of this trial, including quality checks of the data.

The eCRF must be completed shortly after the patient's visit. All requested information must be entered on the eCRF. If an item is not available or is not applicable, it must be documented as such. The completed eCRF must be promptly reviewed, signed, and dated by the investigator or authorized designee. In the event of discrepant data, TRIO will request data clarification from the sites. The sites will resolve the discrepancy electronically in the EDC system. eCRFs and correction documentation will be maintained in the EDC system's audit trail.

At the end of the trial, the investigator will receive patient data for his or her site in a readable format on a compact disc that must be kept with the trial records. Acknowledgement of receipt of the compact disc is required.

The investigator will retain copies of trial documentation for a period of at least 15 years from trial completion. Additional considerations must be made about complying with applicable local laws, guidelines, etc.

9.7 Data Protection

The patient's personal data and Investigator's personal data which may be included in the sponsor database shall be treated in compliance with all applicable laws and regulations. When archiving or processing personal data pertaining to the Investigator and/or to the patients, the sponsor shall take all appropriate measures to safeguard and prevent access to this data by any unauthorized third party. The anonymity of participating patients will be respected with strict adherence to professional standards of confidentiality and applicable privacy rules.

9.8 Confidentiality and Data Protection

All information concerning the trial supplied by TRIO in connection with this trial and/or by any other party collaborating with TRIO, and not previously published, is considered confidential and proprietary information. This information includes the Investigator's Brochure, clinical protocol, workbooks (if applicable), case report forms, assay methods, TRIO technical methodology, and technical and scientific data. This confidential information shall remain the sole property of TRIO and, shall not be disclosed to others without prior written consent from TRIO and shall not be used except in the performance of this trial.

9.9 Insurance of liabilities

If required, the investigator may forward to the Ethics Committee/IRB a copy of the insurance document required by TRIO, in order to cover his/her liabilities, and those of any other participating parties.

9.10 Use of information and publication

All information concerning the trial drug or in connection with this trial, supplied by TRIO and/or by any other party collaborating with TRIO within this trial and not previously published, is considered confidential and proprietary information. This information includes the Investigator's Brochure, clinical protocol, workbooks (if applicable), case report forms, assay methods, TRIO technical methodology, and basic scientific data. This confidential information shall remain the sole property of TRIO the respective collaborating party and, shall not be disclosed to others without prior written consent from TRIO and shall not be used except in the performance of this trial.

To allow for the use of the information derived from this clinical trial and to insure compliance to current regulations, the investigator is obliged to provide TRIO with complete test results and all data developed in this trial. No publication, abstract or presentation of the trial will be made without the approval of the Steering Committee. The Steering Committee will review the manuscript to prevent forfeiture of patent rights to data not in the public domain. Prior to publication, the authorship list will be agreed upon by the Steering Committee. For the purpose of the efficacy and safety analyses, the names on the author list will be given according to the participation in the concept of the trial design as well as accrual input (number of eligible patients accrued) by the investigators at each center. The maximum number of authors will be determined by the publication policy established by the targeted journal. Abstracts and publications will be

submitted to the authors and to the Study Steering Committee at least 30 days prior to the expected date of submission to the intended publisher.

APPENDIX 1 : EASTERN COOPERATIVE ONCOLOGY GROUP PERFORMANCE STATUS SCALE

Grade	Description
0	Fully active, able to carry on all pre-disease performance without restriction.
1	Restricted in physically strenuous activity but ambulatory and able to carry out work of a light and sedentary nature, e.g., light housework, office work.
2	Ambulatory and capable of all self-care, but unable to carry out any work activities. Up and about more than 50% of waking hours.
3	Capable of limited self-care, confined to bed or chair more than 50% of waking hours.
4	Completely disabled. Cannot carry on any self-care. Totally confined to bed or chair.
5	Dead

[figure not shown]
APPENDIX 2 : NYHA CLASSIFICATION

Clinical Evaluation of Functional Capacity of Patients with Heart Disease in Relation to Ordinary Physical Activity

NYHA	Functional Class	Description	Objective Assessment
I	Mild	No limitation of physical activity. Ordinary physical activity does not cause undue fatigue, palpitation or dyspnoea.	No objective evidence of cardiovascular disease.
II	Mild	Slight limitation of physical activity. Comfortable at rest, but ordinary physical activity results in fatigue, palpitation or dyspnoea	Objective evidence of minimal cardiovascular disease
III	Moderate	Marked limitation of physical activity. Comfortable at rest, but less than ordinary activity causes fatigue, palpitation or dyspnoea.	Objective evidence of moderately severe cardiovascular disease.
IV	Severe	Unable to carry out any physical activity without discomfort. Symptoms of cardiac insufficiency at rest. If any physical activity is undertaken, discomfort is increased.	Objective evidence of severe cardiovascular disease.

The Criteria Committee of the New York Heart Association. Nomenclature and Criteria for Diagnosis of Diseases of the Heart and Great Vessels. 9th ed. Boston, Mass: Little, Brown & Co; 1994:253-256

Figure 1 : Trial Scheme - Patient Selection and Treatment

* As described in section 3-Trial Design (IN ADDITION)

## **SAP Changes From Version 1.0 to Version 2.0**

The objective of SAP version 2.0 is to update the SAP version 1.0 to match the updated CRF version 2.2 (dated 29-Jan-2014). Some redefinitions were also applied..

Other noteworthy revisions are described below:

Section #	Changes
10.2	Prior Surgery for Breast cancer and Prior Anti-Tumor Therapy are considered as part of Disease Characteristics rather than Medical History.
10.3	This section is considered as Not Applicable as data dealing with Medical History are not collected anymore in CRF version 2.2.
11.1	Baseline Demographics and Disease Characteristics will be summarized on ITT population only.  Only the treatment emergent adverse events will be considered in the outputs. Therefore, the treatment emergent flag is removed.

## List of Abbreviations

AE	Adverse Event
CI	Confidence Interval
CMH	Cochran-Mantel-Haenszel
CR	Complete Response
CTCAE	Common Terminology Criteria for Adverse Events
DM	Data Management
ECOG	Eastern Cooperative Oncology Group
eCRF	Electronic Case Report Form
EGFR	Epidermal Growth Factor Receptor
ER	Estrogen Receptor
H- score	Immunohistochemistry staining score
HER2	Human Epidermal Growth Factor Receptor 2
ITT	Intent-to-Treat
KM	Kaplan-Meier
LVEF	Left Ventricular Ejection Fraction
MedDRA	Medical Dictionary for Regulatory Activities
MUGA	Multigated Acquisition
NE	Not Evaluated
OCRDC	Oracle Clinical Remote Data Capture
ORR	Objective Response Rate
OS	Overall Survival
PD	Progressive Disease

PFS	Progression Free Survival
PgR	Progesterone Receptor
PR	Partial Response
TTP	Time To Progression
RECIST	Response Evaluation Criteria in Solid Tumors
SAE	Serious Adverse Event
SC	Steering Committee
SD	Stable Disease
TEAE	Treatment Emergent Adverse Event
TLF	Tables, Listings, and Figures
TRIO	Translational Research in Oncology
UE	Un-evaluable
URS	User Requirement Specifications
WHODD	World Health Organization Drug Dictionary

## **1. INTRODUCTION**

This Statistical Analysis Plan (SAP) describes the detailed statistical methodology for executing the statistical analyses to assess the antitumor activity and safety profile of letrozole in combination with afatinib (BIBW2292) versus letrozole alone in the first line treatment of ER+, HER2 negative postmenopausal Advanced Breast Cancer women with low ER expression. The data will be analyzed by TRIO. It is planned that the data from all centers that participate in this study will be used.

## **2. STUDY OBJECTIVES**

### **2.1 Primary Objective**

The primary objective is to compare the progression-free survival (PFS) of the drug combination letrozole plus afatinib (BIBW2292) to letrozole alone in the first line treatment of ER+, HER2 negative postmenopausal Advanced Breast Cancer women with low ER expression.

### **2.2 Secondary Objectives**

The secondary objectives of this study are:

- To compare the Overall Survival (OS) between the two treatment arms
- To compare the Objective Response Rate (ORR) between the two treatment arms
- To compare the Time to Tumor Progression (TTP) between the two treatment arms
- To assess the safety and tolerability in the two treatment arms

### **2.3 Exploratory Objectives**

TRIO plans to examine the molecular profiles of tumor tissue submitted by the subjects to identify factors that may influence biological and clinical responses to afatinib and letrozole including but not limited to Estrogen Receptor (ER) and Progesterone Receptor

(PgR) statuses, H-score and the EGFR related downstream pathways. The analyses performed afterwards will be described in a separate document.

### **3. STUDY DESIGN**

This phase II, multicenter, multinational, open-label, parallel group, randomized study will compare a two-drug regimen of letrozole plus afatinib (BIBW2292) to letrozole alone in the first line treatment of ER+, HER2 negative postmenopausal Advanced Breast Cancer women with low ER expression.

Randomization is stratified by Bone only disease (Yes vs. No) and by Prior neo/adjuvant hormonal therapy (Yes vs. No). Eligible subjects will be randomly assigned in a 1:1 ratio to either:

**Arm A: Continuous regimen of oral letrozole 2.5 mg daily** until progression of disease or any other study treatment discontinuation criteria.

OR

**Arm B: Continuous regimen of oral letrozole 2.5 mg daily plus oral afatinib 30 mg daily** until progression of disease or any other study treatment discontinuation criteria.

Once the subject is discontinued from study treatment and has undergone the End of Treatment visit, the subject will enter into the follow-up phase.

This study also includes an optional exploratory research component. This optional portion is a molecular profiling assay aimed to assess the relationship of antitumor activity with the expression of selected cell cycle-related proteins and other markers that may be identified in the future. Subjects may participate in this study even if they choose not to participate in the sample banking component.

## 4. STUDY ENDPOINT AND COVARIATES

### 4.1 Efficacy Endpoints

#### Progression-Free Survival (PFS)

Progression-free survival (PFS) is defined as the time from randomization until the first evidence of progression as defined by RECIST version 1.1 or death from any cause.

Subjects who have neither progressed nor died will be censored at the day of their last radiographic tumor assessment, if available, or the date of randomization if no post initiation (i.e. post-baseline) radiographic assessment is available. Symptomatic/clinical disease progression (deterioration) without documented radiologic progression will not constitute progression for the purposes of determining PFS.

It is defined as:  $PFS = \text{Date of Progression/Death/Censor} - \text{Date of Randomization} + 1$ .

	Situation	Date of Progression or Censor	Outcome
1	No baseline tumor assessments	Date of Randomization	Censored
2	No post-baseline assessments and no death	Date of Randomization	Censored
3	No documented progression and no death (with a post-baseline tumor assessment)	Date of last tumor assessment	Censored
4	Subject lost to follow-up (or withdrew consent from study participation) before documented progression or death	Date of last tumor assessment	Censored
5	Documented progression	Date of documented progression.	Progressed

		If a tumor assessment was done on multiple days, use the earliest date for that visit.	
6	Death without documented progression	Date of death	Progressed

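### Row 1 of the SAP's PFS table censors a patient without a baseline tumour assessment even if she dies or progresses, contradicting the PFS definition and rows 5 and 6

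*SAP*

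**What the plan says.** SAP 4.1 runs PFS from randomisation to "the first evidence of progression as defined by RECIST version 1.1 or death from any cause". Its censoring sentence is limited to match: "Subjects who have neither progressed nor died will be censored at the day of their last radiographic tumor assessment", or at randomisation if there is no scan after baseline. A six-row table then assigns a date and an outcome:

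| Row | Situation | Date used | Outcome |
|---|---|---|---|
| 1 | "No baseline tumor assessments" | Randomisation | Censored |
| 2 | "No post-baseline assessments and no death" | Randomisation | Censored |
| 3 | Neither progression nor death, with a scan after baseline | Last assessment | Censored |
| 4 | Lost to follow-up or withdrawn "before documented progression or death" | Last assessment | Censored |
| 5 | Documented progression | "Date of documented progression" | Event |
| 6 | "Death without documented progression" | Death | Event |

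The time is the chosen date minus the randomisation date, plus 1. TTP, also in SAP 4.1, takes over the same censoring rules but does not count death. SAP 7 keeps every randomised patient in the ITT population used for efficacy. Neither document says that the rows are read in order or which one prevails.

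**The concern.** Row 1 is the only censoring row with no condition on death or progression. Rows 5 and 6 assign an event without asking for a baseline assessment. For the same patient the table can therefore give two dates and two outcomes, and two programmers could derive different PFS values from it. Coded literally, row 1 turns a death that the definition counts into a censored time of one day. PFS was the planned primary endpoint, so its derivation should give one answer per patient. TTP inherits the overlap between rows 1 and 5.

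**Working it through.** The plan attaches no figure to this rule, so there is none to reproduce. The check is textual, followed by the SAP's own time formula and the effect on a Kaplan-Meier curve.

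**1. Which rows apply to a randomised patient with no baseline assessment?**

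- *She dies without documented progression.* Row 1 gives censoring at randomisation. Row 6 gives an event at death. The definition and the censoring sentence agree with row 6.
- *A progression is recorded.* Row 1 gives censoring at randomisation. Row 5 gives an event, provided that the progression counts as documented. The SAP does not say whether it does.

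**2. Derived values, using PFS = date − randomisation date + 1 (illustrative dates)**

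- Row 1: 0 + 1 = 1 day, censored.
- Row 6, death 90 days after randomisation: 90 + 1 = 91 days, event.
- Row 5, progression at the second 12-weekly scan: 2 × 12 × 7 = 168 days after randomisation, so 168 + 1 = 169 days, event.

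**3. Effect of one such death on her arm's Kaplan-Meier estimate**

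Let n be the arm size, r the number at risk just before her death (including her), and S the estimate at her death date with row 1 applied. If her death is counted, she stays in the earlier risk sets and the estimate is multiplied by (1 − 1/r) at her death.

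- Keeping her in the earlier risk sets cannot lower the estimate before her death, so the drop is at most S/r.
- With no earlier censoring and k others still event-free, the estimates are k/(n − 1) under row 1 and k/n under row 6. The difference is k/[n(n − 1)] = S/n. Earlier censoring of others can only enlarge it.
- Hence S/n ≤ drop ≤ S/r. With no earlier events, S = 1 and the drop is 1/r.

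| Case | Calculation | Drop (percentage points) |
|---|---|---|
| n = 75 (planned, SAP 5.2), no earlier events or censoring | 1/75 | 1.3 |
| n = 75, 37 earlier events, no censoring | 37/74 − 37/75 = 0.500 − 0.493 | 0.7 |
| n = 75, no earlier events, 37 censored earlier (r = 38) | 1/38 | 2.6 |
| n = 10 (assumed), no earlier events or censoring | 1/10 | 10 |
| n = 10 (assumed), no earlier events, 5 censored earlier (r = 5) | 1/5 | 20 |

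Actual arm sizes are not in the documents. Enrolment closed early, so the planned 75 will not apply. The 10-patient rows only show how the effect scales.

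**4. How often could this arise?**

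The number is not given and should be close to zero. Protocol 6.3.2.1 required baseline disease assessment in the 28 days before randomisation. Inclusion criterion 7 and exclusion criterion 6 depend on RECIST classification of the disease, and Protocol 6.1.2 has eligibility checked before randomisation.

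**The case against.** The strongest reply is that the text above the table already settles the death case: PFS includes death from any cause, and only patients without progression or death are censored. On that reading row 1 simply lacks a few words. That is probably what happened, but the table is what a programmer codes, and nothing says that the text overrides it. Reading the rows from the top would make matters worse, because row 1 would then override the endpoint's definition.

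Second, RECIST progression is hard to establish without a baseline. Lesions are identified at baseline, and growth is judged against an on-trial reference (Protocol 6.3.2.4 and 6.3.2.6). This narrows the overlap between rows 1 and 5, mainly to a new lesion seen between two later scans, but does not remove it. It supports stating a decision and does not show which decision is right. The overlap between rows 1 and 6 is untouched, since a death needs no scan.

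Third, the reach is small, and this stands. Protocol 2.1.2 sets the objectives aside and rules out comparison between arms. Protocol 8 contains no efficacy analysis. Under Protocol 6.2 patients now leave the trial when treatment stops, which limits the collection of later deaths, although Table 13 follows adverse events to 30 days after the last dose or 30 November 2018, whichever is earlier. SAP 9.1 sends missing baseline data to data management and lists absent disease assessments among the deviations that may affect the analysis. That makes a case easier to notice but does not say how to derive it. Against this, Protocol 2.1.2 still has the collected data described by arm, Protocol 8 refers descriptive analyses to the SAP, and SAP 11.2 and 11.3 still plan a per-patient PFS listing and a Kaplan-Meier plot.

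**Conclusion.** The concern holds and is minor. Row 1 contradicts the PFS definition, the censoring sentence and row 6 for a patient who dies without a baseline assessment. It also overlaps row 5 without a rule when progression is recorded. For an affected patient the difference is between a 1-day censored time and an event at the true date, such as 91 or 169 days in the illustrations. One such death would lower her arm's curve by between S/n and S/r from that date onward. This is at most 1.3 points at the planned 75 per arm without earlier censoring, and more in a small or heavily censored arm. The expected number of patients is close to zero, and the effect is confined to whatever descriptive PFS output is produced. No direction of bias and no loss of power is claimed.

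**What to change.** In the SAP 4.1 table, add *and no death* to row 1, so that a death without documented progression is an event under row 6.

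In the same row, state whether row 1 or row 5 applies when progression is recorded without a baseline assessment:

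- If row 5 applies, the progression date is the event, whether or not she later dies.
- If such a progression is not accepted as documented, she is censored under row 1 while alive and has an event at death under row 6.

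For TTP, keep row 1 without the death condition, because death is not an event there, and apply the same decision between rows 1 and 5.

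The cost is a few words and one sentence in one table row, plus a small change to the derivation program.

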6.3.2 Efficacy assessments

6.3.2.1 Schedule/details of tumor assessments

Screening/Baseline:

Baseline Disease assessment were performed during screening, within 28 days of randomization of the patient.

Disease assessment at screening was used to determine the nature of lesions (measurable versus non-measurable). Lesions must be clearly identified and documented as Target or Non-Target lesions as per RECIST 1.1.

Baseline assessment included at least:

- Baseline bone scan
- Other bone imaging had to be performed on bone lesions if the investigator intended to follow bone lesions with correlative imaging (e.g. CT with bone window, MRI or plain X-rays).
- CT or MRI scan of the chest, abdomen, and pelvis (CAP)
- Clinical assessment of superficial lesions (including measurement with calliper)
- Any additional imaging as deemed appropriate

Subsequent Disease assessments:

- Every 12 weeks (+/- 1 week) starting from date of randomization
- Whenever disease progression is suspected,
- To confirm a partial or complete response (at least 4 weeks after initial documentation of response). For patients with bone metastases identified at baseline bone scan is required at the time of confirmation of complete response.

Disease assessments will be performed until the end of treatment. The schedule of assessments should be fixed according to the calendar, regardless of treatment interruptions.

Disease assessments will comprise evaluation of all lesions identified at baseline, with the exception of bone lesions in some circumstances (see 6.3.2.2).

The same method of assessment and the same technique should be used to characterize each identified and reported lesion at baseline and during follow-up imaging.

Unless clinically required, it is not mandated to repeat imaging of an area where no lesion was documented at baseline.

Table 10 : Efficacy assessments

Baseline Within 28 days of randomization	Treatment phase until the End of Treatment

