**Time to Progression (TTP)**

Time to progression (TTP) is defined as the time interval from date of randomization to date of the first documented objective tumor progression. Time to progression does not include deaths as events. Subjects who did not progress are censored at the last radiographic tumor assessment (i.e., with a cycle/visit response of CR, PR, SD, PD). If no post-baseline assessment is available, censoring will occur at date of randomization. The same censoring rules will be applied as for PFS, except that death is not considered as an event.

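### SAP 4.1 gives PFS and TTP different censoring dates when the last tumour assessment is not evaluable, while stating that both follow one rule

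*SAP*

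**What the plan says.** SAP 4.1 sets out PFS censoring twice, in prose and in a six-row table.

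- **Prose.** Patients with neither progression nor death are censored at their last radiographic tumour assessment, "or the date of randomization if no post initiation (i.e. post-baseline) radiographic assessment is available".
- **Row 2.** "No post-baseline assessments and no death": censored at randomisation.
- **Row 3.** "No documented progression and no death (with a post-baseline tumor assessment"): censored at the last tumour assessment.
- **Row 4.** "Subject lost to follow-up (or withdrew consent from study participation) before documented progression or death": also censored at the last tumour assessment, with no post-baseline condition.

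None of these mentions evaluability. Under TTP, patients who did not progress are censored at the last radiographic assessment, "i.e., with a cycle/visit response of CR, PR, SD, PD". The same paragraph then adds: "The same censoring rules will be applied as for PFS, except that death is not considered as an event".

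The SAP's only instruction on NE visits is a footnote to the confirmed-response table under ORR. It applies to response confirmation.

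**The concern.** For a patient with neither progression nor death, nothing separates PFS from TTP, so the two should be censored on the same day. The text does not achieve this when the last visit is NE. The PFS wording accepts that visit, the TTP list leaves it out, and the cross-reference says the rules are identical. All three cannot hold together.

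The TTP list has a second gap. Protocol Table 12 gives Non-CR/Non-PD as the overall response when non-target lesions persist without progression, and the list does not contain it. Protocol 4.1 admits patients with bone-only non-measurable disease, and bone-only disease is a stratification factor. The omission therefore falls on a group the trial set out to include.

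Lastly, a patient lost or withdrawn before her first on-study scan fits both row 2 and row 4. Row 2 gives the randomisation date. Row 4, read alone, points to the screening scan.

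At stake is whether the primary endpoint has a single determinate censoring date. The trial is open-label, so a programmer who has to choose a date may do so knowing the treatment arm.

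**Working it through.** **Inputs**

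- Disease assessments every 12 weeks, plus or minus 1 week, counted from randomisation (Protocol 6.3.2.1). Visit k falls on day 84k ± 7.
- Baseline imaging: "Baseline Disease assessment were performed during screening, within 28 days of randomization of the patient" (Protocol 6.3.2.1).
- PFS in days = "Date of Progression/Death/Censor" minus the randomisation date, plus 1 (SAP 4.1).
- NE is a defined overall response in Protocol Tables 11 and 12.

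The plan prints no figure on this point. Its event target is not in dispute and reproduces: with HR = 9/14, two-sided 10% and 80% power, 4 × (1.645 + 0.842)² / (ln 9/14)² ≈ 126.7, so 127 events. The proposed change leaves this target and the 150 patients as they are.

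**Step 1: last visit NE.** Gap = PFS censoring date minus TTP censoring date. TTP is taken to fall back to randomisation when no visit has a listed response.

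- Only post-baseline visit is NE: (84 ± 7) - 0 = 77 to 91 days, nominally 84.
- One NE visit after an evaluable scheduled visit: (84k ± 7) - (84(k-1) ± 7) = 84 ± 14 = 70 to 98 days, nominally 84.
- Two NE visits in a row at the end: nominally 2 × 84 = 168 days.
- Protocol 6.3.2.1 also calls for scans when progression is suspected, and for confirmation of response at least 4 weeks later. Where such scans occur, the gap differs from these figures.

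With one shared definition of an evaluable assessment the gap is 0.

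**Step 2: non-target lesions only.** Take a patient with Non-CR/Non-PD at four scheduled visits and no event. PFS is censored at 4 × 84 = 336 days after randomisation. Read literally, TTP has no qualifying response and is censored at randomisation, a gap of 336 days.

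**Step 3: rows 2 and 4.** For a lost patient with no post-baseline scan:

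| Baseline scan, days before randomisation | Row 4 alone, using the baseline scan | Row 2 or prose |
|---|---|---|
| 0 | 0 + 1 = 1 | 1 |
| 1 | -1 + 1 = 0 | 1 |
| 14 | -14 + 1 = -13 | 1 |
| 28 | -28 + 1 = -27 | 1 |

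Row 4 also does no separate work. A lost patient with a post-baseline scan is already in row 3, and one without is already in row 2.

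**Step 4: does the row 4 date matter to a test?** In one simulated 150-patient data set, ten censored times were moved from day 1 to day -13. The log-rank Z was -1.647 both ways, because neither date leaves the patient at risk at the first event.

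**The case against.** The strongest reply is that the TTP bracket is a gloss. It explains what a radiographic assessment is, using the term the PFS prose also uses, and the next sentences tie the two endpoints together. The list cannot be an exact filter anyway: it includes PD for patients who did not progress and omits Non-CR/Non-PD. This is a fair reading, but it does not settle the matter. If the bracket governs both endpoints, PFS also excludes NE visits, and the PFS text should say so. If it is loose shorthand, nothing says whether NE counts as a response.

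Three stronger conclusions are tempting, and the documents do not support them.

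- **That the SAP prescribes a negative PFS.** It does not. The prose covers everyone without an event and makes no exception for lost patients, and row 2 agrees. A time below 1 day arises only if row 4 is applied alone. Step 4 shows that even this would leave the log-rank result unchanged. It could alter a displayed patient count if times below zero are discarded.
- **That PFS is always censored later than TTP.** The NE gap exists only when the last assessment is NE, and the Step 2 gap only for patients with non-target lesions only. In patients who die without progression, PFS properly runs past the TTP censoring date.
- **That time up to an NE visit is wholly unverified.** In Table 11 an NE visit still requires no new lesion and no non-target progression; in Table 12 it requires no new lesion. Such a visit carries partial evidence.

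The reply on severity stands. Protocol 2.1.2 rules out comparison between arms, and Protocol 8.2 to 8.4 describe no efficacy analysis.

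**Conclusion.** The inconsistency is real and minor. As written, a patient whose last visit is NE has a PFS censoring date about 84 days after her TTP date (70 to 98 days across the two one-NE-visit cases, assuming scheduled visits only). The TTP list, taken literally, also censors at randomisation any non-progressing patient who has non-target lesions only and no CR. The row 2 and row 4 overlap is a drafting fault with no effect on a log-rank result.

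The documents give no frequency of NE visits and no split by arm, so no effect on a median or hazard ratio can be calculated, and none is claimed.

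The practical relevance rests on one assumption: that the SAP's efficacy displays are still produced. Protocol section 8 refers the descriptive analyses to the SAP. The SAP plans PFS medians with numbers at risk (10.5.1), a per-patient listing of PFS and TTP (11.2) and Kaplan-Meier plots of both (11.3). With enrolment closed early, each censoring date carries more weight in those displays than it would among 150 patients.

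**What to change.** Write one rule in SAP 4.1 for both endpoints: a patient without an event is censored at the last evaluable post-baseline radiographic tumour assessment, or at randomisation if there is none. Define evaluable as an overall response of CR, PR, SD or Non-CR/Non-PD, so that NE does not qualify. Apply this in the PFS prose and in row 3. Delete row 4, or make it refer to the rule. In the TTP paragraph, delete the separate list and keep the reference to PFS.

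The cost is a short SAP edit. No new data are needed, and the planned sample size and event target do not change. The downside is that PFS becomes slightly shorter for patients whose last scan is NE, and the partial information in those scans is given up.
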